Duration of IP administration	Once during surgery
Population	184 participants scheduled for total shoulder arthroplasty (TSA)
Study Sites	NYU Langone Orthopedic Hospital
Number of participants	184
Description of Study Agent/Procedure	Injection of 20mL 0.5% Bupivacaine HCL versus 10mL Liposomal Bupivacaine plus 10mL Bupivacaine 0.5% in an Interscalene block for TSA
Reference Therapy	Reference is Bupivacaine 0.5% for Interscalene block
Key Procedures	Interscalene nerve block with Liposomal Bupivacaine + Bupivacaine 0.5%
Statistical Analysis	Intention-to-treat analysis will be performed with mean, t-tests, within and between group ANOVA and linear regression,

CONFIDENTIAL

This material is the property of the NYU School of Medicine and Langone Medical Center. Do not disclose or use except as authorized in writing by the study sponsor

1 Key Roles

Principal Investigator:

[name]

Assistant Professor of Anesthesiology
Department of Anesthesiology, Perioperative care and Pain Medicine
NYU Langone Orthopedic Hospital
NYU Langone Health
[name]
[name]
[contact]

Co-Investigators:

[name]

Professor of Anesthesiology
Department of Anesthesiology, Perioperative care and Pain Medicine
NYU Langone Orthopedic Hospital
NYU Langone Health
[name]
[name]

[name]

Assistant Professor of Orthopedic Surgery
Department of Orthopedic Surgery
NYU Langone Orthopedic Hospital
NYU Langone Health
[name]
[name]

2 Background and Specific Aims

With the growing elderly population, the number of total shoulder arthroplasty (TSA) surgeries is increasing. Nationwide, the total and partial shoulder replacements increased from about 18,000 in 2000 to over 45,000 in 2013 according to the American Academy of Orthopedic surgeons (AAOS). One of the greatest drivers of cost following TSA has been shown to be discharge disposition. Effective pain control after surgery is paramount because it facilitates rehabilitation and decreases hospital length of stay. Additionally, it may increase the likelihood of patients being discharged to their home rather than a rehabilitation or skilled nursing facility.

TSA is a procedure that is well confined within the dermatomal distribution of an interscalene brachial plexus nerve block (ISB), making it an ideal procedure to both evaluate and compare the regional potential of varying agents. Although the analgesic coverage is typically ideal, single shot injection of the long acting

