Occupational and physical therapy progress and activity goals will be reviewed. As per standard of care, motor testing of the operated shoulder and arm will be assessed during these visits. This includes: No weight bearing exercises will be performed as per surgeon's instructions and the nursing staff will continue to obtain VAS pain scores.

[figure not shown]
During the 24-72 hour post-operative period, research staff will visit the patient while they are in the hospital to obtain and verify the pain medication taken. If the patient is discharged before the 72-hour period, the research staff will give the patient a copy of a medication record diary to complete. Additionally, the staff member will call the patient within 1-2 business days to obtain the remaining opioid utilization information.

After discharge, the research staff will continue to follow up with the patient on POD 7, POD 14 and POD 30 to assess pain scores, opioid usage patterns, and functional status. The pain intensity PROMIS assessment will be administered during each phone call. Additionally, on POD 30, participants will complete the Upper Extremity PROMIS form. Research staff will verify documented opioid refills through Epic and pharmacy records.

CONFIDENTIAL

This material is the property of the NYU School of Medicine and Langone Medical Center. Do not disclose or use except as authorized in writing by the study sponsor

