6.1 General Approach

Intention-to treat. The primary analysis will follow the intention-to-treat (ITT) principle in order to evaluate the true outcome of the intervention as experienced by the patient who is blinded to the intervention.

Missing Data. It is anticipated that the data for some subjects will be incomplete for various reasons: missing daily-diary entries, refusal to answer a sensitive question on a questionnaire, onset of illness, loss-to-follow-up, etc. All occurrences of incomplete data will be investigated to carefully document the reasons for the missing data. If the primary outcome (amount of opioid used between 24 and 72 hours after surgery) cannot be ascertained with a reasonable degree of certainty, the patient will be excluded from the study.

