6.2 Analysis of Endpoints

Primary Endpoints:

Opioid utilization (expressed as oral morphine mg equivalents) used during initial 24-72 hours post-operative period after surgery.

Secondary Endpoints:

CONFIDENTIAL

This material is the property of the NYU School of Medicine and Langone Medical Center. Do not disclose or use except as authorized in writing by the study sponsor

Duration of opioid use
Patient reported pain scores (VAS)
Length of stay
Progress with physical therapy
Reported long-term narcotic use at home
Discharge location: home, acute rehab or skilled nursing facility
Documented opioid refills
Adverse events such as respiratory depression, hypoventilation, reintubation, nausea, constipation

The analysis of opioid use, VAS, and PROMIS assessments will rely on a univariate analysis of variance model for mean score. This model is in the class of models commonly known as unirep-ANOVA models. It assumes that the mean score is a function of elapsed time and the treatment regimen assigned. This model considers the fact that the subject's repeated measures are correlated. The fitted model will provide statistical estimates of the mean levels, the treatment-effect differences between mean levels, the standard deviation, the intra-class correlation coefficient, 95% CIs, standard errors (SE), and statistical hypothesis tests. The estimates of means will be used to compute summary criteria such as area under the curve (AUC) for each regimen. All estimates reported will be presented their 95% CIs.

All endpoints will be evaluated as fits the data set with graphical figures such as scatter plots, box-and-whisker plots, and frequency histograms to visualize the distribution of these outcomes and their relationships to covariates and treatment assignment. When appropriate descriptive graphical and tabular methods will also be estimated and presented in a graphical figure.

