10.1 Data Collection and Management Responsibilities

Data collection is the responsibility of the clinical trial staff at the site under the supervision of the site PI. The investigator is responsible for ensuring the accuracy, completeness, legibility, and timeliness of the data reported.

All source documents should be completed in a neat, legible manner to ensure accurate interpretation of data. Black ink is required to ensure clarity of reproduced copies. When making changes or corrections, cross out the original entry with a single line, and initial and date the change. **DO NOT ERASE, OVERWRITE, OR USE CORRECTION FLUID OR TAPE ON THE ORIGINAL.**

Copies of the electronic CRF (eCRF) will be provided for use as source documents and maintained for recording data for each participant enrolled in the study. Data reported in the eCRF derived from source documents should be consistent with the source documents or the discrepancies should be explained and captured in a progress note and maintained in the participant's official electronic study record.

Clinical data (including AEs, concomitant medications, and expected adverse reactions data) and clinical laboratory data will be entered into Redcap. The data system includes password protection and internal quality checks, such as automatic range checks, to identify data that appear inconsistent, incomplete, or inaccurate. Clinical data will be entered directly from the source documents.

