14.3 Medication Usage Record

Medication Record for TSA Surgery

Thank you for participating in our research study and helping us improve pain control for patients undergoing total shoulder arthroplasty (TSA) surgery.

Patient: _____

Pain medication: **Percocet**

Please record the following information in the log below:

1. Time when you take your pain medication
2. How many pills you took at each time
3. Pain score on a scale of 0-10 (0 being no pain and 10 being the worst pain imaginable)
4. Any additional pain medications (such as Advil), therapies (such as ice packs) and side effects (such as itching or nausea).

Time	Number of pills of Percocet	Pain Score (scale of 0-10)	Additional pain medications, therapy or side effects

We will call you within 1-2 business days after surgery to ask for the above information. Additionally, participants can also scan, photograph and email the medication record to [name] at [contact]

Thank you for your participation.

CONFIDENTIAL

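### Opioid use after discharge is self-reported with no check on tablets taken, and the form's call can fall before hour 72; inexpensive changes would make the primary total more even between arms

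*Combined protocol and SAP*

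**What the plan says.** Section 6.2 defines the primary endpoint as oral morphine equivalents "used during initial 24-72 hours post-operative period after surgery". The Protocol Summary and section 2.2 give the whole 72-hour period instead. The point below applies to either window.

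The source of the data changes at discharge:

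- **In hospital** (3.1): "research staff will visit the patient while they are in the hospital to obtain and verify the pain medication taken".
- **After discharge, before hour 72** (3.1): "the research staff will give the patient a copy of a medication record diary to complete". A staff member also telephones to collect the remaining opioid use. Section 3.1 allows one to two business days for this call but does not say whether they run from surgery or from discharge. The form in 14.3 counts them from surgery.
- **Return of the diary** (14.3): patients are asked for its contents on the call, and "participants can also scan, photograph and email the medication record". Return is a choice.
- **External check** (3.1): "Research staff will verify documented opioid refills through Epic and pharmacy records". No count of tablets dispensed or left is described.
- **Next contact** (3.1): POD 7, then POD 14 and POD 30.

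The form has a time column but no date column. Section 6.1 expects "missing daily-diary entries" among the reasons for incomplete data, and excludes patients whose primary outcome cannot be established with reasonable confidence. On length of stay, section 2 says of effective pain control that "it facilitates rehabilitation and decreases hospital length of stay". Section 2.2 says stay might be affected by the combined block, and 6.2 lists it as a secondary endpoint.

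**The concern.** One total is assembled from two sources of unequal reliability, and the join is the moment of discharge. That moment comes after randomisation and may itself respond to treatment. If home doses are recorded less completely than hospital doses, the arm that goes home earlier has more of its window in the weaker source. Its recorded total is then lower even when true use is equal. Blinding the patient and the data collectors does not prevent this, because the difference arises from where the patient is and not from knowledge of the assignment.

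The call schedule makes incomplete home recording a practical possibility. An inpatient is covered by staff visits. A patient already at home may be telephoned before the window closes and then not contacted again until POD 7. With no date column, diary rows may also be hard to place inside the window.

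At stake are a possible false difference on the primary endpoint, and an inability to tell afterwards whether an observed difference arose in hospital data or in home data.

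**Working it through.** **1. Call timing (14.3, counted from surgery, no holidays)**

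| Surgery | Call on | Hour 72 | Call before hour 72? |
|---|---|---|---|
| Mon | Tue or Wed | Thu | Yes |
| Tue | Wed or Thu | Fri | Yes |
| Wed | Thu or Fri | Sat | Yes |
| Thu | Fri or Mon | Sun | Yes if Fri, no if Mon |
| Fri | Mon or Tue | Mon | About hour 72 or later |

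A call at hour 48 leaves (72 − 48)/48 = 50% of the 24-72 h window still to come. A call at hour 24 leaves (72 − 24)/48 = 100%. For a 0-72 h window the shares are 24/72 = 33% and 48/72 = 67%.

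**2. Size of a between-arm effect**

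From the documents: 184 enrolled to give 146 evaluable (4.6), so 146/2 = 73 per arm if losses are equal. Section 6.3 gives no effect size, SD, alpha or power, so 146 cannot be reproduced. Two-sided 0.05 is inferred from the 95% intervals in 6.2.

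Assumed, because the documents give no values:

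- equal true use in both arms, mean 50 and SD 40 MME (CV 40/50 = 0.8);
- use spread evenly over the 48 h window;
- u, the share of home use not recorded;
- h, the share of the window spent at home.

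Recorded mean = true mean × (1 − u × h). As a fraction of the control arm's recorded mean, the SE of the difference is 0.8 × √(2/73) = 0.132. With z the false difference divided by this SE, two-sided rejection is Φ(z − 1.96) + Φ(−z − 1.96).

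Here the liposomal arm is taken to leave earlier. If control left earlier, the sign would reverse.

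| u | h control / liposomal | Recorded, control / liposomal | False difference | z | Two-sided type I error |
|---|---|---|---|---|---|
| 0.1 | 0.50 / 0.75 (12 h) | 0.950 / 0.925 | 2.6% | 0.20 | 5.5% |
| 0.2 | 0.50 / 0.75 (12 h) | 0.900 / 0.850 | 5.6% | 0.42 | 7.0% |
| 0.3 | 0.50 / 0.75 (12 h) | 0.850 / 0.775 | 8.8% | 0.67 | 10.2% |
| 0.3 | 0.25 / 0.75 (24 h) | 0.925 / 0.775 | 16.2% | 1.22 | 23.2% |

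Simulation of the last three rows (gamma-distributed use, individual home shares varying with SD 0.25, t-test, 20,000 trials) gives about 6-7%, 9-10% and 22-23%.

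**3. Sensitivity to CV**

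In SD units the bias is approximately u × Δh / CV, where Δh is the between-arm difference in home share.

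- u = Δh = 0.1, CV 1.0: 0.1 × 0.1 / 1.0 = 0.01 SD.
- u = Δh = 0.3, CV 0.7: 0.3 × 0.3 / 0.7 = 0.13 SD, two-sided error 12%. With CV 1.0 it is 0.09 SD and 8.5%.
- Δh = 0: no bias, error 5%.

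For scale, 73 per arm detects (1.96 + 0.84) × √(2/73) = 0.46 SD with 80% power (power assumed).

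**The case against.** A reader might infer that the endpoint rests after discharge on an unverified log alone, and that the plan is therefore biased towards the liposomal arm. The documents do not support this.

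- A staff call is planned, and the form announces it just before the optional-return sentence. Section 3.1 does not limit the call to reading out the log, and POD 7 also covers opioid use.
- Nothing shows that home reports err low rather than high. No stay data are given. The link from this treatment to stay is a general background sentence plus a statement that stay might be affected.
- Section 6.1 has incomplete data investigated, and excludes outcomes that cannot be established. A missing record therefore gives loss, not a low total. Only a partial record that looks complete produces the bias modelled above.
- The scenarios pair equal true opioid use with a 12 to 24 h shorter stay, although the expected route to earlier discharge is better pain control.
- If stay does not differ, proportional under-recording shrinks mean and SD together and leaves power roughly unchanged.

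Two further inferences also fail. Section 10.1 asks that "Data reported in the eCRF derived from source documents should be consistent with the source documents" or that discrepancies be explained; it does not require the diary back. And 4.6 gives no reason for the 184 − 146 = 38 patients allowed as non-evaluable, so they cannot be attributed to lost home totals.

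All of this stands against a claim of demonstrated bias. It does not remove the change of source at discharge, the absence of a check on tablets taken, or the early call. The call is still self-report, and one made before hour 72 cannot collect doses not yet taken.

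**Conclusion.** The point holds as an inexpensive improvement to data capture. It does not establish that the primary result will be biased. The documents settle three things: verification stops at discharge, diary return is optional with only refills checked externally, and the call as timed on the form falls before hour 72 for Monday to Wednesday operations, with no further contact until POD 7. Since discharge follows randomisation, any home under-recording could differ by arm and would favour whichever arm leaves earlier.

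The size is unknown. With 10% of home use unrecorded and a 12 h gap in stay, the effect is negligible (type I error about 5.5%). With 30% and 12 h it is about 10%. About 23% needs 30% unrecorded and a 24 h gap within a 48 h window, which is extreme. With no gap it is zero. These figures rest on assumed opioid mean and SD, home shares and recording loss, and on 73 evaluable per arm.

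**What to change.** In sections 3.1 and 6.2 and the form in 14.3:

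1. Place the data-collection call for early-discharged patients after hour 72, by moving the planned call or extending its window. State the same timing in 3.1 and 14.3, and write the hour-72 date and time on the form at discharge.
2. Add a date column. Make return of the diary (photo or email) expected of everyone, with the call as back-up.
3. Record the number of opioid tablets dispensed, and ask on that call how many are left. Use dispensed plus any refill minus left as a cross-check, with discrepancies queried by staff blinded to arm, and as a sensitivity analysis. Keep the diary/call total as the primary value: the count is also read out by the patient, and it cannot place doses within the window.
4. Record the data source for each patient, and report the in-hospital and home parts of the primary total by arm, so that a difference confined to the home part is visible.

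Cost: a slightly later call, a few form fields, one extra table, and IRB approval of the amended sections (9.2). Section 14 keeps the form outside the protocol, so changing it needs no protocol amendment. The count can still be wrong if tablets are lost or come from another supply. No visits or patients are added.
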